- 26 Any participant who, on their last order, had an “OK to Use” outcome or “Ask a Doctor” outcome and indicated that the doctor gave them permission to continue treatment will be required to have a study mandated LDL-C retest if they do not have a verified source for their LDL-C retest(s). Participants with a study mandated LDL-C retest will be instructed by the Central Assessor to answer “No” to the LDL retest question. The Central Assessor will review the TASS to ensure the participant entered “No” as instructed. If the participant still entered an LDL-C from the study mandated test, the Central Assessor will instruct the participant to repeat the TASS and reiterate to enter “No” to the LDL-C retest question. The reason for instructing participants to answer “No” to the retest question is because they were instructed to retest and did not follow the DFL or Web App instructions for retesting. Because the Web App was designed to allow individuals who do not retest to complete the study, allowing subjects to enter a study mandated test could potentially lead to incorrect outcomes and, in addition, bias the results of the retest compliance endpoint. Participants who enter an LDL-C value into the TASS assessment

that is an inadequate response to treatment will be instructed through the Web App to repeat the LDL-C retest. If these participants on their last order have an “OK to Use” outcome or “Ask a Doctor” outcome and indicated that the doctor gave them permission to continue treatment, a study mandated LDL-C retest will be required if they do not have a verified source for their repeat LDL-C retest(s). Participants who enter Virtual Visit 2 with a “Do Not Use” outcome or an “Ask a Doctor” outcome but they did not indicate the doctor gave them permission to use the drug or withdrew or discontinued from the study will not undergo study mandated testing.

27 The CMOG clinician will then conduct a follow-up medical and medication history to determine if there were any changes in health during the study.

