As mentioned in [Section 3.2.1](#), during the use phase of the study participants will be asked about their repeat LDL-C test to ensure they are getting an adequate therapeutic response. The participant's behavior with regard to retesting as well as the LDL-C value entered into the Web App contribute to their final use assessment. Participants are permitted to enter any LDL-C value into the Web App and are not told that the values will be source verified until Virtual Visit 2. If they are unable to provide a source document for a value, they will have a SMT. In contrast, the CMOG clinician will only be permitted to enter source verified LDL-C data into the Web App for their assessments. This is done to prevent a CMOG final use assessment based on an inaccurate LDL-C. Following feedback from FDA, the Web App was programmed to take specific actions based on whether a participant retested and based on the result of a retest. The actions are as follows:

- If the participant fails to enter a retest, they can continue to reorder provided they do not indicate within the Web App that they experienced another condition that would prevent them from reordering. Participants who continue to receive an “OK to Use” outcome or an “Ask a Doctor” outcome and indicate that the doctor gave them permission to use the drug, and do not voluntarily retest, will have a study mandated LDL-C test performed prior to Virtual Visit 2. This SMT will be used by the clinician for their assessment but will not be used by the participant since they did not voluntarily get tested.
- If the participant enters an LDL-C value into the Web App, the following can occur:
 - If the value demonstrates an adequate LDL-C response (i.e., $\geq 15\%$ reduction), the participant will proceed in the study and will no longer be prompted to enter an LDL-C into the Web App.
 - If the value demonstrates no change or an increase in LDL-C, the participant will get a “Do Not Use” outcome and will be scheduled for Virtual Visit 2 where all procedures except a SMT will be performed. If the participant fails to bring verification of the LDL-C test that resulted in stopping drug, the CMOG clinician will leave the LDL-C field in the Web App blank. The CMOG use assessment would result in an “OK to Use” outcome. However, when a subject who has continued in the study for 3 or more months fails to obtain a verified LDL-C

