retest for use by the CMOG at Visit 2, an “OK to Use” outcome by the CMOG will be coded as missing since the lack of an LDL-C value means the CMOG can never know for certain that the subject was truly “OK to Use”. The need to recode the CMOG outcome in this instance is a function of the Web App being programmed to allow all subjects to complete the 6 months study regardless of whether they obtained an LDL-C retest. In those situations where the participant has been in the study less than 3 months, a verified LDL-C will not be required for the CMOG to determine an outcome since the DFL allows individuals up to 3 months to obtain an LDL-C retest.

- If the value demonstrates an inadequate LDL-C response (i.e., $\geq 0\%$ and $< 15\%$ reduction), the participant will get an “OK to Use” outcome and be able to order drug, but they will be asked to repeat the LDL-C test. Therefore, individuals with an inadequate response, who proceed to purchase more medication, may have more than one LDL-C value entered into the Web App during the course of the study and the second LDL-C value entered into the Web App could result in one of the following outcomes:
 - If the result is an inadequate response or an increase in LDL-C, the participant will get a “Do Not Use” outcome.
 - If the result is an adequate response, the participant will get an “OK to Use” outcome.
 - If no additional LDL-C value is entered into the Web App, the participant will continue to get an “OK to Use” outcome.

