3.2.9 Eligible for Continuous Treatment

Participants eligible for continuous therapy are defined as those with an “OK to Use” outcome or those with an “Ask a Doctor” outcome who indicated the doctor gave them permission to continue treatment, and they continued to have one of these outcomes at all assessments (initial, reorder and final use). Participants who discontinue or withdraw are not eligible for continuous treatment.

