$$\text{Percentage} = \frac{100 * (\text{Number of participants who correctly self-identify as having an “Ask a Doctor Before Use” warning and speak to a doctor})}{\text{Total number of participants who correctly self-identify as having a “Ask a Doctor Before Use” warning}}$$

The number and percentage of participants who correctly self-identify as having a “Ask a Doctor Before Use” warning and speak to a doctor will be summarized on the PP population overall and by subgroups.

Timeframe for Complying with Ask a Doctor Before Use Warning

As discussed in [Section 3.2.8](#), the data for assessing the Ask a Doctor timeframe will come from the Targeted Medical and Medication History Form at Visit 2. For those participants who correctly self-identify as having an “Ask a Doctor Before Use” warning and contact a doctor, the date from when a participant identifies an “Ask a Doctor Before Use” warning to the date their doctor was contacted will be calculated, in number of days, as follows:

$$\text{Time from having a “Ask a Doctor Before Use” warning to contacting a doctor (in days)} = \frac{\text{(Date doctor contacted – Date of “Ask a Doctor Before Use” warning)}}{+ 1 \text{ Day}}$$

Descriptive statistics for time (in days) from having a “Ask a Doctor Before Use” warning and contacting a doctor will be summarized on the PP population overall and by subgroups.

Evaluations of Effectiveness in Lowering LDL-C in Different Participant Subgroups

For participants determined to be eligible for continuous treatment at Visit 2, the difference in PCFB in LDL-C between participants who had a retest LDL-C value during the course of the study with a verified source and those who did not retest but had a SMT completed at Virtual Visit 2 will be assessed. PCFB will be calculated for each of these participant subgroups in the same manner as the primary LDL-C endpoint. The absolute difference in PCFB between these two subgroups will be calculated and descriptive statistics will be summarized on the PP and AUS ITT population overall and by subgroups.

Evaluation of LDL-C Lowering Relative to Level of Dosing Compliance

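### The eligibility rule can drop self-retesters who enter a poor LDL-C result but not participants who never retested, so the exploratory comparison of the two groups favours self-retesting

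*SAP*

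**What the plan says.** SAP 4.2.4, under the evaluation of LDL-C lowering in participant subgroups, takes participants eligible for continuous treatment at Visit 2. It summarises "the difference in PCFB in LDL-C between participants who had a retest LDL-C value during the course of the study with a verified source" and participants who did not retest but had an SMT at Virtual Visit 2. Percent change from baseline (PCFB) is computed as for the primary LDL-C endpoint. Results are descriptive, on the PP and AUS ITT populations, and both summaries lie inside the eligible set.

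Four other provisions decide who is in that set:

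- **Eligibility (SAP 3.2.9).** A participant needs OK to Use, or Ask a Doctor with the doctor's permission, and the condition is that "they continued to have one of these outcomes at all assessments (initial, reorder and final use").
- **Entered retest values (SAP 3.2.3).** "If the value demonstrates no change or an increase in LDL-C, the participant will get a" Do Not Use outcome. For a second value after an inadequate first one, "If the result is an inadequate response or an increase in LDL-C, the participant will get a" Do Not Use outcome as well.
- **SMT values.** SAP 3.2.3 says of a participant who did not retest: "This SMT will be used by the clinician for their assessment but will not be used by the participant". Protocol Section 8, Step 26 adds: "Participants with a study mandated LDL-C retest will be instructed by the Central Assessor to answer" No to the retest question, and to repeat the assessment if they entered the SMT value.
- **SAP Appendix G.** For Sensitivity Analysis #1, which uses the eligible set, the OK to Use completer who entered no LDL-C (scenario 6) is included with the SMT value, with no condition on that value. The Do Not Use participant with a verified retest (Do Not Use scenario 1) is in the primary LDL-C analysis but out of #1.

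**The concern.** The set in which the two groups are compared is defined partly by the outcome being compared, and the definition does not work the same way in both groups. Suppose two participants both have an LDL-C that did not fall. One tested voluntarily and entered the result; that person is out of the comparison. The other never retested and had an SMT; that person stays, and the poor value counts in the SMT mean. The self-retest mean is then more favourable than the SMT mean even if the two groups respond identically.

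The evaluation of LDL-C lowering in different subgroups is a listed exploratory objective (SAP 1.1), and no version of this comparison without the eligibility restriction is planned. A reader of the table would have no means of separating a difference in response from the effect of the selection rule.

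**Working it through.** **Inputs.** PCFB mean -25%, SD 25%, n = 450, threshold -15%, one-sided alpha 0.025 (SAP 1.3). Non-response means PCFB of 0% or above, and inadequate response means a reduction below 15% (SAP 3.2.3). Normality, the share of non-responders who enter their value, and the correlation between first and repeat values are assumptions; the documents do not give them.

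**Check of the planning figure.** The SAP gives no figure for this comparison. The figure that uses the same mean and SD is the power for the third co-primary endpoint: 10 / (25/√450) = 8.49 standard errors, so power exceeds 0.9999. This agrees with the stated figure of more than 99%.

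**All non-responders enter their value.** Let both groups follow N(-25, 25), so the true difference is zero.

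- P(PCFB ≥ 0) = 1 - Φ(1) = 0.159.
- Mean of those left: -25 - 25 × φ(1)/Φ(1) = -25 - 25 × 0.2420/0.8413 = -32.2.
- SMT group, not truncated: -25.0.
- False difference: -7.2 points.

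**Half of them enter it.** The mean among non-responders is -25 + 25 × 0.2420/0.1587 = +13.1. The self-retest mean is (0.8413 × -32.19 + 0.0793 × 13.13) / 0.9207 = -28.3, a false difference of -3.3 points.

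**Range, all non-responders entering the value.** False difference in points, from -SD × φ(a)/Φ(a) with a = -mean/SD:

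| Mean PCFB | SD 15 | SD 20 | SD 25 |
|---|---|---|---|
| -20% | -2.7 | -5.8 | -9.2 |
| -25% | -1.6 | -4.1 | -7.2 |
| -30% | -0.8 | -2.8 | -5.5 |
| -35% | -0.4 | -1.8 | -4.1 |
| -40% | -0.2 | -1.1 | -2.9 |

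The sign is the same throughout.

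**Adding the second-inadequate-value rule.** This was simulated with two million pairs at mean -25 and SD 25, with correlation 0.5 to 1.0 between first and repeat values. The false difference is about -10 to -11 points if half of the initial inadequate responders enter a repeat value. It is about -13 (-12.7 to -14.0) if all of them do.

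**How visible it would be.** The SAP plans no interval for this contrast, so this is only a scale. Assume 450 participants in the comparison, 60% of them self-retesters (270 and 180). The truncated SD is 25 × √(1 - 0.2876 - 0.2876²) = 19.8. The standard error is √(19.84²/270 + 25²/180) = 2.22, and 7.19/2.22 = 3.24. A 95% interval would exclude zero in about 90% of trials, and in 84% to 92% for self-retest shares of 70% down to 50%. The eligible set may well be smaller than 450.

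**The case against.** **Stakes.** The item is exploratory, with no test or threshold. The groups are self-selected, so the contrast is not causal in any population. The restriction has a stated purpose in Sensitivity Analysis #1, which looks at people expected to continue treatment. All of this stands, and it limits the weight of the point. A reader might infer that the LDL-C efficacy result is affected. It is not: the third co-primary analysis keeps Do Not Use participants with verified values.

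**Scope.** A reader might also infer that every poor responder is removed from the self-retest group and none from the other. The documents do not support that. A single inadequate value leaves the participant OK to Use. Removal follows the value entered, so a non-responder who never enters it stays. Participants who self-tested without a source document also have an SMT if still OK to Use (SAP 3.2.1), and SAP 4.2.4 does not clearly place them in either group. If they count as SMT, that group is partly truncated too, since those who entered a non-response have already left. These points reduce the bias but do not reverse it.

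**Whose outcome.** SAP 3.2.9 does not say whether the participant's or the clinician's outcome defines eligibility. The clinician's Visit 2 assessment does use the SMT value. The response classes for the eligible set in SAP 4.2.2 omit the class at 0% or above that the other LDL-C summaries have, which could mean that the authors expected no such values there. But eligibility also requires reorder outcomes, clinicians make no assessment at reorder (Protocol Section 8, Step 19), and Appendix G refers to the participant's outcome. The participant reading is the better one.

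**Size.** The planning values describe the primary LDL-C analysis regardless of final use outcome. The eligible set excludes discontinuers, so a larger mean reduction, and hence a smaller artefact, is plausible.

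**Conclusion.** The point holds for this exploratory comparison. Eligibility depends on LDL-C response for self-retesters who enter a non-response or a second inadequate value, and does not for participants who never retested. With no true difference, the planned contrast favours self-retesting.

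The direction follows from the documents. The size rests on assumptions and should be read as a range. At mean -25% and SD 25% it is -3.3 to -7.2 points as the share of non-responders entering their value goes from half to all. If all enter it, the range is -0.2 to -9.2 over the means and SDs tabulated. A figure near -13 requires every initial inadequate responder to enter a repeat value as well. The plan does not require that, since without a second value the participant stays OK to Use, so it is an upper scenario.

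A reader might go further and suppose that the sponsor intends to claim better response in self-retesters. Nothing in the available text says so, and the protocol's exploratory objectives are redacted.

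**What to change.** In SAP 4.2.4, for this comparison only:

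- Define the population as participants eligible for continuous treatment plus those with a verified LDL-C whose only reason for ineligibility is an LDL-C-based Do Not Use outcome. Report this in place of the planned version, or at least beside it.
- State that the participant's outcome defines eligibility, and which group holds unverified self-retesters who then had an SMT.
- Keep the most recent verified value as the main rule, as for the primary endpoint. The first verified value is a useful optional supplement, because repeats prompted by a poor first result will tend to look better on the second test.
- Report time from treatment start to the LDL-C test by group. Self-retests can fall anywhere in the use period, whereas SMTs are done for Visit 2.

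The comparison should not be opened to all AUS ITT participants with a verified LDL-C. No SMT is done after a Do Not Use outcome, an Ask a Doctor outcome without permission, discontinuation or withdrawal (Protocol Section 8, Step 22; SAP 3.2.1). People who stopped for other reasons would then enter the self-retest group only, which is a new imbalance.

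The change removes most of the bias, not all: a non-responder without a source document has no verified value to add back. The data are already being collected. The cost is one extra table and a population that no longer matches Sensitivity Analysis #1.

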Overall compliance with dosing will be assessed using three methods: pill count, diary review and number of reorders using the Web App. The first assessment for overall compliance uses the pill count or eDiary. Each participant will have overall compliance assessed and will be considered successfully compliant with dosing if they took between 50% and 120% of their pills. The target threshold for the overall compliance endpoint is an observed point estimate for the percentage of participants falling in the 50-120% range to be at least 50%. In other words, at least half of the participants need to be successfully compliant with dosing. In addition to overall compliance, a longitudinal compliance rate will be calculated to assess compliance with continuous dosing across each study drug reorder supply period. The pill use for this analysis will come from the eDiary. Finally, an additional assessment of longitudinal compliance/persistence will be performed using reorder data from the Web App. This endpoint will evaluate the percentage of users who were eligible for continuous treatment and ordered 180 days of therapy. To be eligible for continuous treatment, the participants must have received an “OK to Use” outcome or an “Ask a Doctor” outcome and indicate the doctor gave them permission to continue treatment, and they continued to have one of these outcomes at all assessments (initial, reorder and final use). Participants who discontinue or withdraw are not eligible for continuous treatment. Success is persistence $\geq 50\%$ similar to the other compliance/persistence endpoints. The rationale for setting the compliance/persistence thresholds at 50% is based on prescription data which shows that after 180 days only about 44% of people continue to refill their prescriptions. Our intention is to show that our approach will be at least as good, if not better, on compliance and persistence than what is observed in the real world ([IQVIA](#)). Additionally, assuming an individual takes the medicine intermittently for the duration of the study, a 50% dosing compliance would equate to taking a 2.5 mg dose of rosuvastatin compared to a 5 mg dose. Based on the clinical trial data, a 2.5 mg dose gives an LDL-C lowering of approximately 35% ([Olsson et al 2001](#)). Therefore, someone taking roughly half of their pills (e.g., a 45-pill count takes about 90 days to use) would still receive excellent efficacy.

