A participant may withdraw from the study at any time at his/her own request or may be withdrawn at any time at the discretion of the investigator for safety, behavioral, compliance, or administrative reasons (e.g., continually delaying visits or interactions, refusing to use the eDiary, intoxication or under the influence of drugs). This is expected to be uncommon. Failure to comply with the dosing regimen in and of itself is not a reason for being withdrawn from the study. If a participant expresses a desire to withdraw from the study, the CMOG will attempt to obtain as much information as possible including final diary data, unused drug returned, and any information on AEs. Withdrawals, by definition, will not have completed Virtual Visit 2 or have sufficient data to determine a final use outcome. In those instances where a participant elects to withdraw, the reason for withdrawal will be documented. Withdrawals occurring after signing the ICF but prior to drug delivery to the participant will be designated as “SS Withdrawal”. Withdrawals occurring following drug delivery to the participant are designated as an “AUS ITT Withdrawal”.

A participant will be considered lost to follow-up if he or she repeatedly fails to complete the scheduled virtual visits and is unable to be contacted by the study team or CMOG.

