3.2.10 Pill Count

At Virtual Visit 2, all administered pill bottles will be returned, and pill count will be assessed. The total number of pills dispensed is based on the number of 45-day or 90-day supplies ordered through the Web App. The number of pills returned is the total number of pills remaining in each of the returned bottles. For those participants who refuse to send back their pill bottles for a final pill count, the option to count the pills with the study personnel via video conference will be given. For those participants who have lost one or more of their pill bottles, the eDiary data will be utilized to reconcile compliance with dosing.

Because there may be instances in which a participant continues study medication when they should not have (i.e., participant experiences “Stop Use,” “Do Not Use,” or “Ask a Doctor” warning) but does not stop medication, in order to properly assess compliance with continuous dosing, the intended duration of treatment will be used rather than the actual duration of treatment. The intended duration of treatment is as follows:

Intended Duration of Treatment =	(Intended Treatment Stop Date – Date Participant Received First Supply of Study Drug) + 1 Day
----------------------------------	---

where the date of intended treatment stop will be the date when the medication was intended to be stopped (i.e., the date of “Stop Use” warning, the date of the “Do Not Use” warning, the date of the “Ask a Doctor” warning in situations where the participant did not confirm the doctor gave them permission to use the drug, the date of discontinuation or withdrawal, or for participants who did not receive one of the previous outcomes, the date of Visit 2).

Data listings will be provided for participants TASS initial study drug order and their overall study drug accountability.

3.2.11 eDiary

The eDiary will be used to gather minimal and unbiased data on the participant's use of the IP. The information to be gathered will include dosing (date/time and amount of IP taken), adverse

events (changes in health), and medication changes. The participant will record the unique ID from the study drug bottle to confirm receipt of the product.

At the 60-day and 120-day planned telephone contacts, the eDiary will be reviewed to determine if “Stop Use” criteria may be present and to ask about any changes in health.

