In assessing supply period compliance, the total number of pills dispensed in supply period i will be either 45 or 90 based on the supply ordered and the total number of pills taken is determined based on the information recorded in the eDiary. The start date for assessing compliance in the eDiary will be the first day that the participant records taking the medication. From the start date, supply periods for evaluation of the eDiary are calculated based on the supply ordered. Therefore, the first supply period will include next 45 days for a 45-day supply and the next 90 days for a 90-day supply. The next supply period will start immediately after the first supply period ends, and the duration is based on supply. This method for determining the dates in the eDiary that are assessed for dosing relative to the supply periods will continue until the subject completes Virtual Visit 2 or has an event for which early stopping of therapy is required. In other words, the duration of treatment in the supply period for evaluation in the eDiary can be less than 45 or 90 days in those situations where the participant experiences an event that requires stopping therapy. Thus, the intended duration of treatment for supply period i will be calculated as follows:

Intended Duration of Treatment in Supply Period i =	(Intended Treatment Stop Date in Supply Period i – Date Participant Received First Supply of Study Drug in Supply Period i) + 1 Day
--	--

where the date of intended treatment stop in supply period i will be the date when the entire supply of medication was intended to be used by the participant (assuming one tablet is taken per day) or when the medication was intended to be stopped (i.e., the end date of intended supply period based on number of pills ordered, the date of “Stop Use” warning, the date of “Do Not Use” warning, the date of discontinuation or withdrawal).

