4.2.3 Analysis of Secondary Efficacy Variables

Secondary efficacy analyses will be conducted on the AUS ITT or PP populations as specified below.

Cholesterol Retesting

During the use period of the study, participants will be told through the Web App and transactional emails to retest their LDL-C within 3 months. Participants who should retest are those who were eligible for continuous treatment. The percentage of participants who are eligible for continuous treatment and have a cholesterol retest within 6 months of starting medication that was verified at Virtual Visit 2 will be calculated as follows:

$$\text{Percentage} = \frac{100 * (\text{Number of participants who are eligible for continuous treatment and had a cholesterol retest within 6 months after starting medication that was verified at Visit 2})}{\text{Total number of participants who are eligible for continuous treatment}}$$

The number and percentage of participants who are eligible for continuous treatment and have a cholesterol retest within 6 months of starting medication that was verified at Virtual Visit 2 will be summarized on the PP population overall and by subgroups. Those participants with an unverified cholesterol retest value at Visit 2, and thus required study mandated testing, will not be included in the numerator for this endpoint. Participants with multiple retests will be included in the numerator for this endpoint if at least one of the retests is a non-study mandated verified retest. That is, at least one of the retests has a Source Type equal to “Verified source” on the

Visit 2 Diagnostic Report. The total number of participants who are eligible for continuous treatment will serve as the denominator for the percentages.

The target threshold for this endpoint is that the observed PE needs to be at least 60% in the overall analysis. There are no target thresholds for the subgroup analyses.

An additional analysis of cholesterol retesting will be conducted on those participants in the AUS ITT population. The percentage of participants who had a cholesterol retest within 6 months of starting medication that was verified at Virtual Visit 2 will be calculated as follows:

$$\text{Percentage} = \frac{100^* \text{ (Number of participants who had a cholesterol retest within 6 months after starting medication that was verified at Visit 2)}}{\text{Total number of participants in the AUS ITT Population}}$$

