Descriptive statistics for PCFB in verified LDL-C at Visit 2 for those participants eligible for continuous treatment will be summarized by level of overall compliance (>0 - <50%, 50-120%, and >120%) in the PP population overall and by subgroups, and for those participants with supply period compliance between 50% and 120% across all supply periods, in the PP population overall and by subgroups. The calculations for overall compliance and supply period compliance will be calculated using the same method as previously described in [Section 4.2.3](#).

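### The exploratory table of LDL-C change by dosing compliance counts pills up to Visit 2, although a self-retested LDL-C may have been drawn months earlier

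*SAP*

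**What the plan says.** **Exposure.** SAP 4.2.4 (evaluation of LDL-C lowering relative to level of dosing compliance) states that percent change from baseline (PCFB) in verified LDL-C "will be summarized by level of overall compliance (>0 - <50%, 50-120%, and >120%) in the PP population". It adds: "The calculations for overall compliance and supply period compliance will be calculated using the same method as previously described in" Section 4.2.3. There, overall compliance is pills taken divided by intended duration of treatment. SAP 3.2.10 starts that duration at first delivery. It ends it at a warning, discontinuation or withdrawal, or, "for participants who did not receive one of the previous outcomes, the date of Visit 2". The supply periods of SAP 3.2.11 likewise form a sequence that "will continue until the subject completes Virtual Visit 2 or has an event for which early stopping of therapy is required".

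**Who is included.** SAP 3.2.9: "Participants who discontinue or withdraw are not eligible for continuous treatment". SAP 3.1: "Failure to comply with the dosing regimen in and of itself is not a reason for being withdrawn from the study". For most people in this table the compliance window therefore closes at Visit 2, and those who stay in the study but miss pills remain in it.

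**Response.** SAP 4.2.2 uses the most recent verified LDL-C, taken from a reorder assessment and verified at Visit 2; it need not be drawn then. Participants are "told through the Web App and transactional emails to retest their LDL-C within 3 months". SAP 3.2.1 allows a draw at any time from the start of drug. SAP 3.2.3 says that prompting for a retest ends once a reduction of at least 15% has been entered. A study-mandated test near Visit 2 is done only where there is no verified self-retest.

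**The concern.** A statin effect on LDL-C reflects tablets taken before the blood draw. A compliance measure that continues past the draw mixes the relevant exposure with later dosing that cannot have influenced the value. SAP 4.2.2 itself notes that retest values arrive at varying times during the use period. Section 4.2.4 nevertheless sets no window ending at the draw and does not stratify by draw date. The nearest analysis, self-retest against study-mandated test, is not crossed with compliance.

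At stake is the reading of one named exploratory objective (SAP 1.1). If participants lapse after an early and favourable retest, their well-dosed response may be shown as the response of low compliers, and LDL-C lowering will look less dependent on dosing than it is.

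**Working it through.** The documents give no expected effect or sample size for this table, so there is no planned figure to reproduce. The check has three parts.

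**1. When does a participant move into the row below 50%?** Take 180 days to Visit 2 and a draw on day t. Let A be compliance to the draw and B compliance afterwards.

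Overall compliance = [A·t + B·(180 − t)] / 180

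Setting this equal to 50% gives B = (90 − A·t) / (180 − t).

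| Draw day | A | B below which overall compliance is under 50% |
|---|---|---|
| 45 | 100% | 45/135 = 33% |
| 60 | 100% | 30/120 = 25% |
| 75 | 100% | 15/105 = 14% |
| 90 | 100% | 0/90 = 0%, so it cannot happen |
| 90 | 80% | 18/90 = 20% |

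Example: a draw on day 60 with 90% of pills taken before it and 25% after. Pills taken = 0.90 × 60 + 0.25 × 120 = 54 + 30 = 84, and 84/180 = 46.7%. The planned table puts this person below 50%; compliance up to the draw was 90%.

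**2. How much of the window lies after the draw?** A day-90 draw leaves 90/180 = 50% and a day-45 draw leaves 135/180 = 75%.

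**3. What does this do to the contrast between rows?** A simulation used 200,000 participants per setting. LDL-C lowering depended on A only: 0% at no pills, 35% at half the pills (Protocol 3.1, the 2.5 mg figure) and 45% at full dosing (Protocol 2.3.2), linear between these points, with residual SD 15 (assumed). Compliance before and after the draw followed assumed beta distributions with correlation 0.3 to 0.9. The difference in mean PCFB between participants below and at or above 50% was compared under the two groupings.

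With compliance falling from mean 80% (SD 20%) to 60% (SD 30%) and correlation 0.6:

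| Draw day | Grouped by compliance to draw | Grouped as planned | Ratio |
|---|---|---|---|
| 60 | 16.8 points | 7.7 points | 0.46 |
| 90 | 16.9 points | 9.9 points | 0.59 |

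Ratio of planned to aligned contrast over all settings tried (falling: means of 80% or 85% dropping to 60%; stable: same mean and spread before and after):

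| Draw day | Compliance falls | Compliance stable |
|---|---|---|
| 45 to 90 | 0.17 to 0.66 | 0.45 to 0.98 |
| 120 | 0.61 to 0.80 | 0.99 to 1.06 |

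For a draw near day 165, as with a study-mandated test, the ratio was 0.88 to 1.04 over both patterns.

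**The case against.** Several points on the other side stand.

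- The low row needs a marked, unreported lapse. Declared discontinuations are excluded, and Protocol 8 and 8.1 provide a day-120 call and an alert after more than 7 days without diary activity. A participant fully dosed to a day-90 draw cannot fall below 50%.
- Flattening is not general. With stable compliance and draws from day 120 it is absent in the simulation, and study-mandated tests are little affected.
- The size rests on assumed compliance patterns and draw dates.
- An eDiary measure has its own error. SAP 4.2.3 treats missing entries as missed doses, so people who take pills but skip the diary would be placed in the low row. SAP 4.1.3.1 sets a missing day of a diagnostic test to the first of the month. Pill count avoids the first problem.

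A reader might infer three stronger things that the documents do not support.

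- *That the all-supply-periods summary is contaminated in the same way.* It reports only participants at 50-120% in every supply period. A late lapse removes a member, but there is no low-compliance row for that person to enter.
- *That the table tests, or is bound to confirm, the half-dose statement.* Protocol 3.1 says that "someone taking roughly half of their pills (e.g., a 45-pill count takes about 90 days to use) would still receive excellent efficacy". Someone at 50-60% falls in the 50-120% row beside full compliers, so these bands do not isolate half dosing under either window.
- *That this is the only exposure-response analysis planned.* Protocol 9.4.2.3 is redacted and SAP 6.1 refers to a supplemental SAP, so this cannot be established.

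**Conclusion.** The mismatch of windows follows from the stated definitions, and nothing in the SAP corrects it. It matters for participants whose analysed LDL-C is an early verified self-retest and whose dosing then declines. Self-retesters would be at least 60% of those eligible for continuous treatment if the secondary retest target is met; that is a target, not a forecast.

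For draws by day 90 with falling compliance, the planned contrast was 0.17 to 0.66 of the aligned one in the assumed settings. These figures show direction and plausible range only; they are not estimates for this trial. The analysis is descriptive with no threshold, so this is a worthwhile improvement and not a flaw that threatens any co-primary or secondary conclusion.

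**What to change.** In SAP 4.2.4, before database lock:

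1. Add a table of PCFB by compliance computed from eDiary dose dates, from first dose to the draw date of the LDL-C used, with the existing three bands. No fixed look-back window is needed.
2. Keep the existing pill-count table, and also show it separately for verified self-retests and study-mandated tests (or by draw timing).
3. Report the aligned table beside the pill-count table. Repeat it among participants with adequate diary completion, defined in advance, and flag draw dates whose day was imputed.

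The cost is SAP wording, one new table with its diary-completion repeat, and one split display. The eDiary already records the date and amount of each dose (SAP 3.2.11), and SAP 4.1.3.1 already handles dates of diagnostic tests, so participants carry no extra burden. The remaining downside is error from diary gaps and imputed days, which is why the aligned table supplements the pill-count table and does not replace it.
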